8.4. Treatment Compliance

Treatment compliance with all study-related medications should be emphasized to the subject by the site personnel. Subjects will bring all bottles of unopened, empty, and unused study drug with them to each study visit. The appropriate study personnel will maintain records of study drug receipt and dispensing. Any discrepancy regarding the dose administered and the reason for the discrepancy will be recorded in the electronic case report form (eCRF). At each clinic visit, patients will be questioned about their compliance with study drug administration, and their dosing diary should be reviewed. Bottles of study drug, including all bottles of unopened, partially opened, or empty bottles cannot be destroyed or returned to the depot until a monitor reviews and verifies all tablet counts for compliance. Compliance with pembrolizumab will also be documented in the medical record and monitored by the principal investigator of its designee.

8.5. Randomization and Blinding

Not applicable.

8.6. Duration of Treatment

The subject will continue to receive study treatment as long as the subject is receiving benefit from treatment and has not met any criteria for study withdrawal (Section 6.6). If the subject discontinues study treatment, the treatment phase will end and the subject will enter the follow-up phase (Section 12).

8.7. Treatment After Initial Evidence of Radiographic Disease Progression

Version Date: 11/09/2017

Immunotherapeutic agents such as pembrolizumab and epacadostat may produce antitumor effects by potentiating endogenous cancer-specific immune responses. The response patterns seen with such an approach may extend beyond the typical time course of responses seen with cytotoxic agents and can manifest as a clinical response after an initial increase in tumor burden or even the appearance of new lesions.

If radiologic imaging shows progressive disease (PD), tumor assessment should be repeated ≥ 4 weeks later to confirm PD, with the option of continuing treatment for clinically stable subjects while awaiting radiologic confirmation of progression. Clinically stable may be defined by the following criteria:

- Absence of signs and symptoms indicating disease progression
- No decline in ECOG performance status
- Absence of rapid progression of disease
- Absence of progressive tumor at critical anatomical sites (eg, cord compression) requiring urgent alternative medical intervention

In determining whether the tumor burden has increased or decreased, investigators should consider all target lesions as well as non-target lesions. Subjects who are deemed clinically unstable are not required to have repeat imaging for confirmation. If radiologic progression is confirmed, then the subject will be discontinued from study treatment as specified in the Protocol, and the first radiographic evidence of PD should be the date of progression. If radiologic progression is not confirmed, then the subject should resume/continue study treatment and have their next scan according to the Protocol-specified schedule.

9. DOSE DELAYS/ MODIFICATIONS

9.1. Criteria and Procedures for Dose Modifications and Interruption

In some circumstances, it may be necessary to temporarily interrupt study treatments as a result of AEs that may have an unclear relationship to the study drug(s). If an interruption is necessary both study treatments should be interrupted.

Treatment with both study drugs should be withheld for drug-related Grade 4 hematologic toxicities, non-hematological toxicity \geq Grade 3 (including laboratory abnormalities) or selected \geq grade 2 immune-related toxicities (see section 9.2), and severe or life-threatening AEs.

Pembrolizumab must be permanently discontinued for Stevens Johnson Syndrome (SJS) or Toxic Epidermal Necrolysis (TEN)

Table 1 summarizes the dose administration guidance for pembrolizumab and epacadostat that should be implemented with the indicated related AEs. Additional information related to dose changes for epacadostat and pembrolizumab for specific AEs can be found in Section 9.2.

Columbia University Medical Center Herbert Irving Comprehensive Cancer Center Version Date: 11/09/2017

 Table 1: Dose Modification Guidelines for Drug-Related Adverse Events

Toxicity	Grade	Hold	Timing of	Dose Schedule for	Treatment Restart	Discontinue Subject
		Treatment (Y/N)	Treatment Restart	Epacadostat	Pembrolizumab	
Hematologic Toxicity	1, 2, 3	No Yes	N/A Toxicity resolves to ≤ Grade 1 or baseline	N/A Reduce dose to 50 mg PO BID. If 50 mg PO BID is not tolerated, then epacadostat should be discontinued.	N/A Restart at same dose for the following events: Grade 4 neutropenia lasting ≤ 7 days, Grade 4 lymphopenia or leukopenia. For all other Grade 4 Hematologic toxicities treatment with pembrolizumab may not be restarted.	N/A Toxicity does not resolve within 6 weeks of last infusion. Permanent discontinuation should be considered for any severe or life-threatening event.
Non-Hematologic	1	No	N/A	N/A	N/A	N/A
Toxicity Note: Exception to be treated similar to Grade 1 toxicity: - Grade 2 alopecia - Grade 2 fatigue - Grade 3 rash in the absence of desquamation, without mucosal involvement, not requiring systemic steroids, and that resolves to Grade 1	2	Consider holding for persistent symptoms	Toxicity resolves to ≤ Grade 1 or baseline	Restart at same dose for non-immune related AEs *See section 9.2 for management of immune-related AE's that may require dose reductions. If dose reduction is required: Reduce dose to 50 mg PO BID. If 50 mg PO BID is not tolerated, then epacadostat should be discontinued.	Restart at same dose *See section 9.2 for management of immune- related AE's that may require dose reductions.	Toxicity does not resolve within 6 weeks of last infusion. Permanent discontinuation should be considered for any severe or life-threatening event.
within 14 days * See section 9.2 for immune-related AE's	3	Yes	Toxicity resolves to ≤ Grade 1 or baseline	Reduce dose to 50 mg PO BID. If 50 mg PO BID is not tolerated, then epacadostat should be discontinued.	Restart at same dose	Toxicity does not resolve within 6 weeks of last infusion. Permanent discontinuation should be considered for any severe of life-threatening event.
	4	Yes	Discontinue treatment	Treatment with epacadostat may not be restarted	Treatment with pembrolizumab may not be restarted	Toxicity does not resolve within 6 weeks of last infusion. Permanent discontinuation

Columbia University Medical Center Herbert Irving Comprehensive Cancer Center Version Date: 11/09/2017

			should be considered for any severe of life-threatening event.

Note: Subjects who experience a recurrence of the same severe or life-threatening AE at the same grade or greater treatment should be discontinued from study treatment.

Version Date: 11/09/2017

9.2. Procedures for Subjects Exhibiting Immune-Related Adverse Events

This section is meant to apply to suspected immune-related adverse effects (irAEs) from epacadostat, pembrolizumab, or the combination. Immune-related AEs may be defined as an AE of unknown etiology, associated with drug exposure and consistent with an immune phenomenon. Immune-related AEs may be predicted based on the nature of the pembrolizumab or epacadostat compounds, their mechanism of action, and reported experience with immunotherapies that have a similar mechanism of action. Special attention should be paid to AEs that may be suggestive of potential irAEs. An irAE can occur shortly after the first dose or several months after the last dose of treatment.

Recommendations for management of specific immune-mediated AEs such as pneumonitis, enterocolitis, hepatitis, dermatitis, neuropathies, endocrinopathies, and other immune-mediated AEs are detailed in the sections below.

9.2.1. Procedures and Guidelines for Pneumonitis

Subjects with symptomatic pneumonitis should immediately stop receiving pembrolizumab and epacadostat and have an evaluation. The evaluation may include bronchoscopy and pulmonary function tests to rule out other causes such as infection. If the subject is determined to have study drug—associated pneumonitis, the suggested treatment plan is detailed in Table 2.

Table 2. Recommended Approach to Handling Noninfectious Pneumonitis.

	Withhold/ Discontinue Pembrolizumab and Epacadostat	Guidance for Restarting Study Treatment	Supportive Care
Grade 1	No action.	N/A.	Intervention not indicated.
Grade 2	Withhold pembrolizumab and epacadostat.	First episode of pneumonitis: • If improves to near baseline: • Decrease the dose of epacadostat to 50 mg BID, and for pembrolizumab restart at same dose and schedule for subsequent cycles. • If not improved after 2 weeks or worsening permanently discontinue pembrolizumab. Second episode of pneumonitis: • Permanently discontinue pembrolizumab and epacadostat if upon rechallenge subject	Systemic corticosteroids are indicated. Taper if necessary.

Columbia University Medical Center Herbert Irving Comprehensive Cancer Center Version Date: 11/09/2017

		develops pneumonitis ≥ Grade 2.	
Grade 3 and 4	Discontinue pembrolizumab and epacadostat.	Not applicable. Any exceptions require PI approval.	Systemic corticosteroids are indicated. The use of infliximab may be indicated as appropriate.

9.2.2. Procedures and Guidelines for Enterocolitis

Subjects should be carefully monitored for signs and symptoms of enterocolitis (such as diarrhea, abdominal pain, mucus or blood in stool, with or without fever) and of bowel perforation (such as peritoneal signs and ileus). In symptomatic subjects, infectious etiologies should be ruled out and endoscopic evaluation should be considered for persistent or severe symptoms. Recommendations for management of enterocolitis are shown in Table 3.

Table 3. Recommended Approach to Handling Enterocolitis.

	Withhold/ Discontinue Pembrolizumab and Epacadostat	Guidance for Restarting Study Treatment	Supportive Care
Grade 1	No action.	N/A.	All subjects who experience diarrhea should be advised to drink liberal quantities of clear fluids. If sufficient oral fluid intake is not feasible, fluid and electrolytes should be substituted via IV infusion. An antidiarrheal can be started.
Grade 2	Withhold pembrolizumab and epacadostat.	May return to treatment if improves to Grade 1. If AE resolves ≤ Grade 1 or baseline within 4 weeks, subject may restart at the same dose and schedule for both pembrolizumab and epacadostat. For an AE that does not resolve ≤ Grade 1 or baseline in 4 weeks, epacadostat should be reduced as per Table 1, but pembrolizumab may be restarted at the same dose and schedule. If AE does not resolve within 6 weeks, study treatment with	An antidiarrheal should be started. If symptoms are persistent for > 1 week, systemic corticosteroids should be initiated (eg, 0.5-1 mg/kg per day of prednisone or equivalent). When symptoms improve to ≤ Grade 1, corticosteroid taper should be started and continued over at least 1 month.

Version Date: 11/09/2017

		both study drugs should be discontinued.	
Grade 3 and 4	Discontinue pembrolizumab and epacadostat.	Not applicable. Any exceptions require PI approval.	Treatment with systemic corticosteroids should be initiated at a dose of 1 to 2 mg/kg per day of prednisone or equivalent. Systemic corticosteroids are indicated. The use of infliximab may be indicated as appropriate. When symptoms improve to ≤ Grade 1, corticosteroid taper should be started and continued over at least 1 month.

9.2.3. Procedures and Guidelines for Hepatitis

Liver function tests (hepatic transaminase and bilirubin levels) should be monitored and signs and symptoms of hepatotoxicity should be assessed before each dose of pembrolizumab and epacadostat. In subjects with hepatotoxicity, infectious or malignant causes should be ruled out and frequency of LFT monitoring increased until resolution. Recommendations for management of hepatitis are shown in Table 4.

Table 4. Recommended Approach to Handling Hepatitis.

	Withhold/ Discontinue Pembrolizumab and Epacadostat	Guidance for Restarting Study Treatment	Supportive Care
Grade 1	No action.	N/A.	Increase frequency of LFT monitoring to twice per week until LFTs return to baseline.
Grade 2	Withhold pembrolizumab and epacadostat.	If AE resolves to ≤ Grade 1 or baseline within 4 weeks, subject may restart at the same dose and schedule for both pembrolizumab and epacadostat.	Increase frequency of LFT monitoring to twice per week until LFTs return to baseline. If elevation persists for > 1 week, systemic
		For an AE that does not resolve ≤ Grade 1 or baseline within 4 weeks, epacadostat should be reduced as per Table 1, but pembrolizumab may be restarted at the same dose and schedule.	corticosteroids should be initiated (eg, 0.5 mg/kg per day of prednisone or equivalent). When symptoms improve to ≤ Grade 1, corticosteroid

Columbia University Medical Center Herbert Irving Comprehensive Cancer Center Version Date: 11/09/2017

		If AE does not resolve within 6 weeks, study treatment with both study drugs should be discontinued.	taper should be started and continued over at least 1 month.
Grade 3 and 4	Discontinue pembrolizumab and epacadostat.	Not applicable. Any exceptions require PI approval.	Increase frequency of LFT monitoring to every 1-2 days. Treatment with systemic corticosteroids should be initiated at a dose of 1 to 2 mg/kg per day of prednisone or equivalent. When symptoms improve to ≤ Grade 1, corticosteroid taper should be started and continued over at least 1 month.

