9.2.4. Procedures for Immune-Mediated Dermatitis

Monitor subjects for signs and symptoms of dermatitis such as rash and pruritus. Unless an alternate etiology has been identified, signs or symptoms of dermatitis should be considered immune mediated. Recommendations for management of dermatitis are shown in Table 5.

Table 5. Recommended Approach to Handling Dermatitis.

	Withhold/ Discontinue Pembrolizumab and Epacadostat	Guidance for Restarting Study Treatment	Supportive Care
Grade 1	No action.	N/A.	For mild to moderate dermatitis, such as localized rash and pruritus, treat symptomatically. Administer topical or systemic corticosteroids if there is no improvement of symptoms within 1 week.
Grade 2	No action	N/A.	For mild to moderate dermatitis, such as localized rash and pruritus, treat symptomatically. Administer topical or systemic corticosteroids if there is no improvement

Version Date: 11/09/2017

			of symptoms within 1 week.
Grade 3 and 4	Withhold epacadostat and pembrolizumab in subjects with moderate to severe signs and symptoms of rash. Permanently discontinue epacadostat and pembrolizumab in subjects with Stevens-Johnson syndrome, toxic epidermal necrosis, or rash complicated by full thickness dermal ulceration or by necrotic, bullous, or hemorrhagic manifestations.	If AE resolves to ≤ Grade 1 or baseline within 4 weeks, subject may restart at the same dose and schedule for both pembrolizumab and epacadostat. If rash is mild and Grade 3 only based on BSA, and resolves without oral steroids, treatment may be restarted at the previous dose. For an AE that does not resolve to ≤ Grade 1 or baseline within 4 weeks, epacadostat should be reduced as per Table 1, but pembrolizumab may be restarted at the same dose and schedule. If AE does not resolve within 6 weeks, study treatment with both study drugs should be discontinued.	Administer systemic corticosteroids at a dose of 1 to 2 mg/kg per day of prednisone or equivalent. When dermatitis is controlled, corticosteroid tapering should occur over a period of at least 1 month.

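### Table 4 (Grade 2 hepatitis) and Table 5 (Grade 3 and 4 dermatitis) give a 4-week pembrolizumab restart step with no resolution condition, and Table 5 leaves a Grade 4 restart route that conflicts with Table 1

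*Combined protocol and SAP*

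**What the plan says.** Table 4 (Grade 2 hepatitis) and Table 5 (Grade 3 and 4 dermatitis) share a three-step restart rule. If the event resolves within 4 weeks, both drugs resume unchanged. For the middle step, Table 4 says that for an event which "does not resolve ≤ Grade 1 or baseline within 4 weeks, epacadostat should be reduced as per Table 1, but pembrolizumab may be restarted", with dose and interval unchanged; Table 5 has "does not resolve to ≤ Grade 1 or baseline within 4 weeks, epacadostat should be reduced as per Table 1, but pembrolizumab may be restarted". If the event is unresolved at 6 weeks, both drugs stop.

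For Grades 3 and 4 together, Table 5 opens with "Withhold epacadostat and pembrolizumab in subjects with moderate to severe signs and symptoms of rash". Permanent discontinuation is reserved for Stevens-Johnson syndrome (SJS), toxic epidermal necrolysis (TEN), and rash with full-thickness ulceration or necrotic, bullous or hemorrhagic features.

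Table 1 in Section 9.1 times restart after Grade 2 or 3 non-hematologic toxicity at "Toxicity resolves to ≤ Grade 1 or baseline". After Grade 4 it says "Treatment with pembrolizumab may not be restarted", and it bars epacadostat in the same way. On the link between the two sections, Table 1 carries the note "See section 9.2 for immune-related AE's", and the text of Section 9.1 says "Additional information related to dose changes for epacadostat and pembrolizumab for specific AEs can be found in Section 9.2".

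**The concern.** Taken word for word, the middle step applies to an event that is still active at week 4, and it allows a checkpoint inhibitor to be given again. Table 4 shows how awkward that is: its supportive-care column starts the steroid taper only once symptoms reach Grade 1 or lower, so a patient on the literal path could be re-dosed before the taper may begin. An infusion cannot be withdrawn, and Section 4.3 reports a long half-life and target engagement beyond 21 days.

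Separately, a patient with Grade 4 rash and none of the listed complications could restart under Table 5 without PI approval, although Table 1 forbids it. A site treating hepatitis or rash will naturally open the organ-specific table.

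**Working it through.** This is mainly a comparison of text. The plan states no figure to reproduce.

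**Step 1: is restart tied to resolution where the 4-week sentence appears?**

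| Table and row | Improve-first opening | 4-week sentence | 6-week stop |
|---|---|---|---|
| 3, enterocolitis, Grade 2 | Yes | Yes | Yes |
| 4, hepatitis, Grade 2 | **No** | Yes | Yes |
| 5, dermatitis, Grades 3 and 4 | **No** | Yes | Yes |
| 6, neuropathy, Grade 2 | Yes | Yes | Yes |
| 7, endocrinopathy, Grades 2 and 3 | Yes | Yes | Yes |

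The opening in Table 3 is "May return to treatment if improves to Grade 1"; Tables 6 and 7 add baseline as an alternative. With that line, the 4-week sentence can only concern late resolution. Without it, the condition has to be inferred. The gap is confined to weeks 4 to 6.

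**Step 2: what happens at Grade 4?**

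- Table 1, non-hematologic: neither drug may be restarted.
- Tables 2, 3, 4 and 6 (Grades 3 and 4) and Table 7 (Grade 4): discontinue both, with exceptions only by PI approval.
- Table 5: withhold, then restart under the three-step rule, with no PI approval, unless a listed complication is present.

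Table 7 already separates Grade 3 from Grade 4. Table 5 does not.

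**Step 3: does either section override the other?** Table 1 points to Section 9.2 for immune-related events, and Section 9.1 presents Section 9.2 as additional. Neither statement ranks them.

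**Step 4: how many patients?** The documents give no rate for events unresolved at 4 weeks or for uncomplicated Grade 4 rash. The nearest inputs are the pembrolizumab monotherapy counts in Section 11.1.7:

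- Autoimmune hepatitis: 19/2799 = 0.679%; × 23 = 0.156.
- Severe skin reactions: 46/2799 = 1.643%; × 23 = 0.378.
- Sum, if no patient has both: 65/2799 = 2.322%; × 23 = 0.534 expected.

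This counts any such event, not the defect. It includes hepatitis of all grades and may include SJS, TEN and complicated rash, which the tables handle elsewhere. It also takes monotherapy rates for a combination. The share reaching the 4-week clause is unknown. As an assumption only, 10% gives 0.534 × 0.10 = 0.053 patients and 50% gives 0.534 × 0.50 = 0.267.

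**Step 5: exposure per affected patient.** Weeks 4 to 6 span 14 days. With 21 days between infusions, that is at most one 200 mg pembrolizumab dose, plus up to 14 × 2 = 28 epacadostat doses of 50 mg.

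**The case against.** The strongest reply is that the protocol, read as a whole, does not permit re-dosing an active event. Section 9.1 tells sites to withhold both drugs for drug-related non-hematologic toxicity of Grade 3 or above and for selected immune-related toxicity of Grade 2 or above. The disputed sentence itself refers to Table 1, where the reduced epacadostat dose sits beside a restart time set at resolution. The three steps also make best sense as a sequence: early resolution, late resolution, none. Restarting an unresolved event at week 4 only to stop it at week 6 would be odd. Table 1 adds a stop for toxicity not resolved within 6 weeks of the last infusion, which may narrow the window further. Liver tests before each dose, twice-weekly liver monitoring and investigator withdrawal also protect patients.

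Most of this stands for the first point. A reader might infer that the plan clearly authorizes pembrolizumab during ongoing hepatitis or dermatitis; the documents do not support that. What remains is two rows that omit a condition their sister tables state, with no rule on precedence.

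On Grade 4, it can be said that Table 5's withhold sentence speaks of moderate to severe rash, that the worst presentations are already permanent stops, and that nothing shows how much Grade 4 dermatitis is left. The last two are fair limits on size. But the row is labelled for both grades and its restart column does not distinguish them, so the conflict with Table 1 remains. A reader might also infer that Table 5 is the only irAE table by which a Grade 4 patient could return to treatment. That is too strong, because Tables 2, 3, 4, 6 and 7 allow PI-approved exceptions.

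**Conclusion.** Both points hold in limited form. The first is ambiguous wording, confined to weeks 4 to 6, with late resolution the likely intent. The second is a direct conflict between Table 5 and Table 1, limited to Grade 4 dermatitis without the listed complications.

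This is a low-frequency patient-safety correction for the next amendment. The expected number is well under one patient of 23. That rests on monotherapy rates carrying over to the combination and on an unknown share of events reaching the clauses, so no probability for the defect itself can be drawn from the documents. A reader might infer a reason to doubt the efficacy result. There is none: sample size, stopping boundary and error rates of the Simon design do not depend on these rows.

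**What to change.** 1. In Table 4 Grade 2 and Table 5 Grade 3, open the restart cell with the line used in Table 3, "May return to treatment if improves to Grade 1", adding baseline as in Tables 6 and 7.
2. In the same two cells, reword the middle step: if the event resolves to Grade 1 or lower, or to baseline, after 4 but within 6 weeks, epacadostat is reduced as in Table 1 and pembrolizumab may resume unchanged. Keep the 6-week stop.
3. Split the last row of Table 5. Grade 3 keeps the restart guidance; Grade 4 becomes discontinuation of both drugs.
4. Add one sentence to Section 9.1 saying whether Table 1 or Section 9.2 prevails for immune-related events. This also settles whether PI-approved Grade 4 exceptions are allowed. The choice needs care: Table 1 allows restart after a resolved Grade 3 event, whereas Tables 2, 3, 4 and 6 discontinue at Grade 3.

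The cost is a few lines of text, with no extra visits, procedures or patients. Epacadostat reductions do not increase, because the current sentence already reduces it after 4 weeks. The downside falls on two kinds of patient: one unresolved at 4 weeks waits up to 2 more weeks for restart or discontinuation, and one with uncomplicated Grade 4 rash stops treatment.
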